### **3. Sample Size, Statistics, Selection and Withdrawal of Subjects**

#### *Sample Size:*

No formal power calculation was performed as the development of the MSIT was part of a feasibility study. In total, 150,000 patient medical records were examined by MSIT, which resulted in 2,922 probable veterans being identified. These were matched on age and gender to a probable civilian cohort of 2,922. Hence, a total sample of 5,844. Due to resource limitations we did not apply the Tool to the full database of the SLaM NHS Foundation Trust. It is expected that 20% of the sample will have Consent for Contact. This estimate is based on previous studies.

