## Study Synopsis

Full Title	Validating the Military Service Identification Tool in its ability to correctly identify civilians and those who have served in the military.
Short Title/Acronym	Military Service Identification Tool
Protocol Version number and Date	Version 1 (02/03/2020)
Study Duration	12 months
Study Design	Questionnaire, interview or observation study
Sponsor/Co-sponsors	King's College London
Chief Investigator	[name]
IRAS number	278987
Primary objective	The principal research question is to ascertain whether individuals identified by the Military Service Identification Tool have or have not served in the military (Armed Forces).
Secondary objective (s)	N/A
Number of Subject	Expected sample n=1168. This represents an estimation that 20% of our cohort (n=5844) will have given consent for contact.
Main Inclusion Criteria	Only those participants who formed part of our original study will be screened for eligibility. This corresponds to 2,922 probable veterans and 2,922 civilians. The following inclusion criteria will apply: 1. Participant are listed as 'Alive' in the NIHR Maudsley Biomedical Research Centre Clinical Record Interactive Search database; 2. Participants aged 18 years and older; 3. Participant has given Consent for Contact; 4. Participant has a valid postal address or telephone number; 5. Participants have capacity to consent.
Statistical Methodology and Analysis	Aggregation of data to estimate accuracy of the Military Service Identification Tool

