To address the time it took to identify veterans and improve sensitivity and reach we developed the MSIT, and it proved to be quicker, more accurate and cheaper than the manual method. The Tool was designed to detect military service, not just veteran status. We took a systematic approach to developing and testing the MSIT. We used different subsets of all the electronic healthcare records available to us, to ensure the MSIT was developed and trained on a different set of electronic healthcare records (named the training dataset). Subsequently the MSIT was verified on another subset of the data (named the gold standard dataset) to ensure it would still be able to identify veterans if a different set of electronic healthcare records would be used.

We managed to identify 2,922 veterans in the electronic healthcare records when applying MSIT to inspect 150,000 individual records. The MSIT took only 20 minutes to go through all these records and had an identification rate of 88% when compared to the manual approach. We also matched these veterans to 2,922 non-veterans based on age and gender to compare their mental health treatment pathways.

Despite the success of our initial developments we have faced a significant barrier that may prevent the widespread, dissemination, roll-out and implementation of the MSIT. Various academics and stakeholders (e.g. NHS England,

Cobseo) are interested in the MSIT. However, they have highlighted an important limitation, namely it is still unclear whether the veterans identified by the MSIT are ‘actual’ veterans. MSIT identifies veterans based on the notes provided by the clinician in the electronic healthcare record. It is also important to understand if higher rates of physical and mental health are represented in a veteran population compared to civilians. By including both samples – civilian and veteran – we’re ensuring that fair comparisons are able to be made. This There is currently no opportunity to verify their veteran status. For example, no service number is provided in their medical records.

Therefore, to overcome these limitations and to demonstrate that the MSIT is correctly identifying military service (serving personnel, veterans or civilian) it is important to reach out to those who have been identified to ask about their previous Service.

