#### *Participant Eligibility:*

Only those participants who formed part of our original study will be screened for eligibility. This corresponds to 2,922 probable veterans and 2,922 civilians.

The following inclusion criteria will apply:

1. Participant are listed as ‘Alive’ in the SLaM BRC Clinical Record Interactive Search database;
2. Participants will be aged 18 years and old;
3. Participant has given Consent for Contact;
4. Participant has a valid postal address or telephone number;
5. Participants have capacity to consent.

The following exclusion criteria will apply:

Participants will be excluded if a clinician is required to be notified of the research prior to contact, as this may indicate at risk participants. Further participants who are not fluent in spoken English will be unable to take part in the study due to inability to understand the participant information and consent form. Therefore, non-English speaking participants will not be included in this study.

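### The only predicted-civilian sample was age- and gender-matched to the flagged veterans, so its crude error rate need not describe the 147,078 records that MSIT left unflagged

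*Protocol*

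**What the plan says.** The full title in the Study Synopsis sets the aim: "Validating the Military Service Identification Tool in its ability to correctly identify civilians and those who have served in the military". Predicted civilians are therefore part of what is being validated.

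Section 3 (Sample Size) describes the source: "In total, 150,000 patient medical records were examined by MSIT, which resulted in 2,922 probable veterans being identified". It then says how the predicted civilians were chosen: "These were matched on age and gender to a probable civilian cohort of 2,922". The Introduction (The current study) gives the reason for the match: "We also matched these veterans to 2,922 non-veterans based on age and gender to compare their mental health treatment pathways".

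Section 3 (Participant Eligibility) closes the frame: "Only those participants who formed part of our original study will be screened for eligibility. This corresponds to 2,922 probable veterans and 2,922 civilians". The Synopsis gives the size: "Expected sample n=1168. This represents an estimation that 20% of our cohort (n=5844) will have given consent for contact". Its entry for statistical methodology reads, in full: "Aggregation of data to estimate accuracy of the Military Service Identification Tool".

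The protocol does not name NPV, sensitivity or a count of missed veterans. It does not say that results will be carried over to the other unflagged records, and it mentions no weighting or standardisation.

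**The concern.** A sample matched on age and gender to the flagged group takes on that group's age and gender mix. This suits a comparison of treatment pathways. It does not give a representative sample of the records that MSIT classed as civilian. If missed service among unflagged people differs by age or gender, the crude share of predicted civilians who report service is a weighted average with the wrong weights for the unflagged records as a whole.

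The Introduction says that MSIT was built partly to improve sensitivity and reach, and that outside stakeholders want evidence before roll-out. A reader is likely to apply a reported accuracy for civilians to unflagged patients in general, and then to ask how many veterans the tool misses. The matched sample answers that question only after reweighting. The second weighting problem is the sampling ratio. The two predicted groups enter the study 1:1, whereas the scanned records split about 1:50.

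**Working it through.** **Inputs from the protocol.** 150,000 records examined; 2,922 flagged; 2,922 matched predicted civilians; 20% expected to have consent for contact.

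**The plan's own figures.**
- Cohort: 2 × 2,922 = 5,844, as stated.
- Expected sample: 0.20 × 5,844 = 1,168.8, stated as 1,168.
- Unflagged records: 150,000 − 2,922 = 147,078.
- Matched civilians as a share of these: 2,922 / 147,078 = 2.0%.
- Unflagged to flagged: 147,078 / 2,922 = 50.3.
- Contactable predicted civilians: 0.20 × 2,922 ≈ 584, before non-response. Each one stands for 147,078 / 584 ≈ 252 unflagged records.

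**Assumptions, because the documents give no age or gender mix and no error rates by stratum.** Two gender strata; unflagged records 50% male; matched sample a share *s* male, with *s* = 0.8 or 0.9; service in a proportion *m* of unflagged men and *f* of unflagged women; PPV 88%. The protocol's 88% is an identification rate relative to the manual method. It is not stated to be a PPV.

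**Formulae.**
- Crude false-omission rate (1 − NPV) = *s·m* + (1 − *s*)·*f*
- Rate in the unflagged records = 0.5*m* + 0.5*f*
- Missed veterans = 147,078 × rate
- Sensitivity = 0.88 × 2,922 / (0.88 × 2,922 + missed veterans)

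| *m*, *f* | Crude rate (*s* = 0.8 to 0.9) | Unflagged rate | Missed: crude vs unflagged | Sensitivity: crude vs unflagged |
|---|---|---|---|---|
| 2%, 0.2% | 1.64–1.82% | 1.10% | 2,412–2,677 vs 1,618 | 52–49% vs 61% |
| 4%, 0.5% | 3.30–3.65% | 2.25% | 4,854–5,368 vs 3,309 | 35–32% vs 44% |
| 8%, 1% | 6.60–7.30% | 4.50% | 9,707–10,737 vs 6,619 | 21–19% vs 28% |

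Worked line for 4%, 0.5% and *s* = 0.8: 0.8 × 0.04 + 0.2 × 0.005 = 0.033. Then 147,078 × 0.033 = 4,854, and 2,571 / (2,571 + 4,854) = 35%.

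**No bias and reversal.** With 2% in both genders, the crude and unflagged rates are both 2.0%. With 2% in men, 3% in women and *s* = 0.85, the crude rate is 0.85 × 0.02 + 0.15 × 0.03 = 2.15% against 2.50%, so the crude figure now understates missed service.

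**Sampling ratio.** Take *m* = 2%, *f* = 0.2%, *s* = 0.9 and PPV 90%.
- Sensitivity read straight from the 1:1 sample: 0.90 / (0.90 + 0.0182) = 98.0%.
- Matched rate applied to 147,078 records: 2,630 / (2,630 + 2,677) = 49.6%.
- Standardised rate applied to 147,078 records: 2,630 / (2,630 + 1,618) = 61.9%.

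For sensitivity, ignoring the 1:1 ratio does more harm than the matching.

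**Precision.** With 584 respondents, 19 reports of service give 3.3%, Wilson 95% interval 2.1% to 5.0%. That interval contains the 2.25% of the unflagged records in the second scenario. Across the six cells in the table, the unflagged rate lies inside the interval around the crude rate in three.

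**The case against.** The strongest reply is that the protocol never makes the inference being criticised. Section 2.1 asks whether people identified by MSIT have served, and uses the errors to refine the algorithm. Weighting and standardisation are often left to a SAP, and none is at hand here. Matching on two recorded variables can be undone later wherever the strata overlap. All of this stands, and it limits the point to a conditional one.

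A reader might infer that the civilian error rate is certainly wrong for the unflagged records and will mislead about missed veterans. The documents do not support that. They do not say how past service varies by age or gender. What matters is service missed by the tool, which also depends on how well the notes record service in each stratum. The bias could be zero or could run the other way. Under the assumed male excess it makes MSIT look worse than it is, so it does not flatter the tool. At the expected sample size, sampling error is often as large.

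Standardisation also has limits. Respondents must be alive, have consented to contact, have capacity, be fluent in English and need no prior clinician notification. Age-gender weights do not remove that selection, and strata absent from the matched sample cannot be standardised at all.

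What the reply does not remove is that the sampling frame is fixed in the protocol. The protocol sets a civilian aim, describes the analysis as aggregation, and does not say which population the civilian result describes. That statement belongs beside the sampling frame.

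**Conclusion.** The point holds in conditional form. By design, the crude error rate among predicted civilians applies to unflagged records with the flagged group's age and gender mix, and it is not a design-based estimate for all 147,078. In the three assumed male-excess scenarios it overstates missed service by about 47% to 65% (3.30 / 2.25 = 1.47; 1.82 / 1.10 = 1.65) and lowers implied sensitivity by roughly 7 to 12 percentage points. Those sizes rest wholly on assumed gender mixes, stratum rates and PPV, and the documents fix neither size nor direction. If sensitivity or overall accuracy is read from the 1:1 sample without weighting, that error is larger and of opposite sign in the example shown (98.0% against 61.9%). This is a cheap improvement to the protocol and does not invalidate the study.

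**What to change.** In section 3:

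1. State that the predicted-civilian result applies to unflagged records with the age and gender mix of the flagged group.
2. Report PPV and NPV separately by predicted group, in place of one pooled accuracy figure from the 1:1 sample.
3. Add an NPV directly standardised to the age-by-gender distribution of the 147,078 unflagged records, over the strata that overlap. Name any strata that cannot be standardised.
4. Base any sensitivity or missed-veteran count only on that standardised NPV, weighted to the 2,922:147,078 ratio.
5. State that these figures remain conditional on consent for contact, capacity, English fluency and response.

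The cost is a short paragraph and one age-by-gender tabulation of records already scanned. No new participants are needed. The downside is wider intervals for the standardised NPV where strata are thin.

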#### *Participant Eligibility:*

Only those participants who formed part of our original study will be screened for eligibility. This corresponds to 2,922 probable veterans and 2,922 civilians.

The following inclusion criteria will apply:

1. Participant are listed as ‘Alive’ in the SLaM BRC Clinical Record Interactive Search database;
2. Participants will be aged 18 years and old;
3. Participant has given Consent for Contact;
4. Participant has a valid postal address or telephone number;
5. Participants have capacity to consent.

The following exclusion criteria will apply:

Participants will be excluded if a clinician is required to be notified of the research prior to contact, as this may indicate at risk participants. Further participants who are not fluent in spoken English will be unable to take part in the study due to inability to understand the participant information and consent form. Therefore, non-English speaking participants will not be included in this study.

#### *Withdrawal:*

Participants are able to withdraw at any point throughout the study up until data analysis. To ensure the participants do not feel unduly burdened by the requirements of the study at any time, they will be reminded of the voluntary nature of their participant, and that they do not need to answer the question and can withdraw from the research at any time. Once a participant has withdrawn from the study, no further contact will be made. Data from withdrawn participants will not be used in the analyses.

Any protocol deviations or violations will be reported to [name] (Chief Investigator) who will act accordingly. If the protocol deviation/violation relates to a participant, they will be withdrawn from the study and appropriate support given (ie. contact by the study clinical team). If the deviation/violation relates to a member of the research team, the NHS Research Ethics Committee and Research and Development will be informed.

#### **4. Study procedures**

Participants will be asked to complete a single questionnaire via a bespoke study website or take part in a short telephone interview.

##### *Informed Consent Procedures:*

Once eligible participants have been identified a Post-Doctoral Research Associate (to be appointed) will, in the first instance, send an email to the participant informing them of the study and asking for consent to the main research question (question 1). Informed content will be obtained prior to any questionnaires or procedures being employed. This will be performed either via the study website or via telephone. Time and date of consent will be recorded alongside a unique study identifier. Participants will be informed that participant is voluntary, that non-participant or withdrawal from the study will not affect their medical care in anyway. Prior to consent being sought, participants will be given time to read and consider the Participant Information Sheet.

##### *Questionnaire Approach:*

Where an email address is not present, a letter will be sent instead, where an email and postal address are not present, the Post-Doctoral Research Associate (to be appointed) will make contact via telephone. Through all forms of communication, participants will be directed to record their response via the study website using a proxy\_id, which is unique to the participant. If participants do not respond after 2 weeks a maximum of 3 attempts to contact the participant using contact information will be made. If we are not able to make contact, they will be removed from the study.

No personal information will be retained on the website, and participants will be required to provide two unique sets of 'identifiers' to log-in. If a participant fails to complete the online questionnaire or would prefer to undertake the study via telephone, a research assistant will make contact. The Post-Doctoral Research Associate (to be appointed) will log participant responses via the study website.

##### *Risk and Burdens:*

We do not anticipate their being any consequences for taking part in this research. However, there is a potential for participant to have negative perceptions towards the concept of military service due to negative experiences in some way. To manage and mitigate these risks, we will adopt the following process:

- 1) The Post-Doctoral Research Associate (to be appointed) employed on the study will have relevant research and clinical experience on how to deal with distressed participants;
- 2) The Post-Doctoral Research Associate (to be appointed) will be trained to encourage the participant to seek help if they are experiencing problems;
- 3) A formal risk protocol will be implemented to ensure that participants who are deemed at risk are appropriately managed;
- 4) For those who are seriously distressed, or deemed at risk, advice will be sought from and as appropriate a call back will be offered by [name], Clinical Psychologist at Combat Stress.

In terms of participant burden, it is estimated that to take part in the study will take no more than 15 minutes. If during the telephone discussion the participant become distressed, the Post-Doctoral Research Associate (to be appointed) will halt the discussion and re-arranged to an alternative time or day. Additionally, to ensure the participants do not feel unduly burdened by the requirements of the study at any time, they will be reminded of the voluntary nature of their participation, and that they do not need to answer the question and can withdraw from the research at any time.

##### *Screening Procedures:*

Except applying the eligibility criteria described previously, participants will not undergo any screening.

##### *Treatments and Follow-up:*

This study does not seek to test any intervention or treatment. We will not perform any follow-up, nor require the participant to provide any further information above and beyond the questionnaire.

*End of Study Definition:*

Once all participants have been contacted using the stated procedure, or after 12 months, whichever comes first, the study will be defined as complete. Participants who have provided an email address will be randomised and winners selected. They will be contacted within 3 months of the study completing.

## **5. Assessment of Safety**

It is possible, but unlikely due to the nature of interaction, that some participants may perceive the interview as distressing or upsetting as we are asking about their military service. It will be stressed to participants during the telephone discussion, email or via post that they do not need to answer the question and are able to decline to partake in the study. The Post-Doctoral Research Associate (to be appointed) contacting the participants will be trained to signpost wherever needed and will be able to act as a listener. A robust risk protocol has been developed in collaboration with SLaM and BRC and [name] (Clinical Psychologist at Combat Stress) to ensure that the Post-Doctoral Research Associate (to be appointed) understands how to respond to a situation. This risk protocol includes key contact information for a range of charitable organisations. It is anticipated that a participants GP manages any identified risk but where that is not possible for any reason, then participants who are seriously distressed or deemed at risk then advice will be sought from and as appropriate a clinical call back offered to participants by [name], Clinical Psychologist at Combat Stress.

## **6. Study oversight arrangements**

The study proposal has undergone extensive review and evaluation within the research team. Study conduct and progress will be monitored by a steering committee representing the research team.

## **7. Ethics & Regulatory Approvals**

This application will be reviewed by the NHS Research Ethics Committee and has received approval from the Research and Development office.

## **8. Data Handling**

Data collected for this study will be encrypted and stored on a secure server maintained by the sponsor organisation and will not identifiable by participant name. The bespoke website for this study will be developed prior to data collection and will use servers located in London, England. The information stored on this system will be:

1. Proxy ID: A unique identifier will be created to allow users to ‘log-in’ and complete the questionnaire. The mapping key to link responses and contact details will be held by the SLaM BRC Research Administrator.
2. Questionnaire responses: Participant questionnaire responses will be recorded in the system and will be saved with the ‘proxy id’ identifier.
3. Prize draw: Participants are able to provide an email address to enter the prize draw. This will be saved in a separate database. At no time will the ‘proxy id’ and email address be linked.

Upon completion of data collection, all data will be downloaded from the server and the server be decommissioned. At any time, up until data analysis, participants can withdraw from the study.

The research team will keep legible and accurate documents to ensure thorough documentation of study conduct. The highest degree of confidentiality will be maintained for managing data collected throughout the course of the study. However, to meet legal responsibilities we will permit authorised representatives of the health authorities to examine records, to satisfy quality assurance reviews, audits and evaluations of study safety and progress.

For data analysis, the non-identifiable data acquired will be downloaded and stored on a secure network managed by SLaM BRC. Only the immediate research team will have access to data collected with the Chief Investigator [name] being the custodian of the data. Data will be used to assess the performance of MSIT, and further refine the Tool to improve classification rates.

This study will be compliant with the principles of the Declaration of Helsinki, compliant with the Data Protection Act (2018) and follow local and national regulations.

